We propose a randomized, crossover, outpatient sleep restriction study with 2 phases of 6 wk each. Sixty -six men and pre-menopausal women, age 20-40 y, BMI 20-34.9 kg/m^2, who have at least one parent with BMI >27 kg/m^2 (if participant BMI is 20-24.9 kg/m^2), will be recruited from the New York City area. Participants who will be recruited to participate in this study will habitually sleep 7-9 h/night, will be free of any current and past sleep and psychiatric disorders, including eating disorders, and will not have diabetes or CVD. The sleep durations will be the participant's regular bed- and wake-times during the habitual sleep (HS) phase and HS minus 1.5 h in the sleep restriction (SR) phase. During the HS phase, participants will be asked to follow a fixed bedtime routine based on their screening sleep schedule. During the SR phase, participants will be asked to keep their habitual wake time constant but delay their bedtime to achieve a reduction of 1.5 h in total sleep time. Two weeks prior to randomization and during washout periods, participants will wear an actigraph (Micro Motion Logger Sleep Watch, Ambulatory Monitoring, Inc., Ardsley, NY) and keep a sleep diary to verify sleep duration and sleep-wake schedule. In addition to achieving an average sleep of 7-9 h/night, per wrist actigraphy, participants will only be enrolled if they achieve 7 h of sleep for at least 10 of the 14 nights of screening and have <4 nights with <6 h of sleep. At randomization, a urine pregnancy test (for women) and drug screen will be performed. Participants will be asked to abstain from caffeine and alcohol intake for 24 h prior to the start of each study phase. Between study phases, if participants have not returned to baseline sleep patterns, an additional 2-4 wk washout period will be provided. In general, washout periods will be 6 wk in duration. This washout length enhances the likelihood that women will be in the same phase of their menstrual cycle at the start of each experimental phase. On the first day of each study phase (baseline), participants will come to Irving Center for Clinical and Translational Research (CTSA) at Columbia University in the morning after an overnight, 12-h fast. Participants will have anthropometric measurements taken, will provide a fasting blood sample, and will then be taken to the department of Radiology to undergo MRI scanning to assess body composition. Participants will begin the fixed bedtime routine that night. These baseline measurements will be repeated at endpoint, 6 wk later. Body weight and waist circumference will be measured weekly, fasting blood and urine samples will be taken at baseline, week-3, and endpoint, during adherence check visits. Brain responses will be assessed using two fMRI paradigms (resting state and task-based) at wk 6, 1 h before the participant's self-reported usual dinner time. The resting state paradigm and intrinsic functional connectivity (iFC) analysis will assess treatment effects on reward and interoception-related neuronal circuitry. During the resting state scan (2 runs, each ~ 5 mins), participants will focus on the fixation cross in the center of the screen. Wakefulness and compliance with eyes-open instructions will be monitored via an eye-tracking camera and verbal reminders given before every run. Pulse and respiration rates will be measured using MRI-compatible non-invasive physiological monitoring equipment. Food intake will be assessed at baseline, wk 3, and wk 6 by 3-d food records (2 weekdays and one weekend day) using an electronic app or by hand if the participant does not have a smart phone. EE will be assessed

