Sample size determination. We will enroll 66 participants and expect 50 to complete the study. This drop-out rate accounts for participant non-compliance. In our previous Sleep Study, our completion rate was 90%. We expect a larger drop-out rate in the proposed study due to the longer duration of each treatment phase, and we also anticipate dismissing some participants due to non-compliance. Each participant will undergo 2 study phases, and each response variable will be measured at least once per phase. Thus, for each response measure we will have at least  $50 \times 2$  paired observations. We have analyzed preliminary data consisting of a number of measurements from 2 overweight women from our Pilot Study. Based on preliminary data analysis we have estimated an effect size (mean paired difference) of  $0.69 \pm 0.36$  g for fat mass and an effect size (mean paired difference) of  $0.91 \pm 0.65$  g for weight gain. This translates to very large effect sizes of 1.92 (fat mass) and 1.4 (weight gain) for paired t-tests. With these effect sizes we have more than 99% power for paired t-tests.] We have estimated the EI effect size to be  $295.9 \pm 116.3$  kcal [8]. The effect size for a paired t-test (effect size divided by the standard deviation) for a paired t-test is >2, which is a very large effect size for paired t-test. This means with  $50 \times 2$  paired samples, we have >80% power for paired t-test. In [name] et al. 2011 [8], we also reported an effect size of  $20.7 \pm 6.8$  g for fat intake and an effect size of  $57.9 \pm 32.6$  g for carbohydrate intake. This translates to very large effect sizes of 3.04 and 1.78, respectively for fat and carbohydrates for paired t-test. With these effect sizes we have >80% power for paired t-test. Moreover, using the R^2 value from our linear model analysis of [name] et al. 2011, we determined that we have >80% power for proposed linear mixed model analyses (as described in statistical plan) with energy balance, fat and carbohydrate intakes. Thus, we have very good power overall, which will be useful in our primary analyses as well as in exploring sex differences. Statistical plan. Exploratory data analyses for physiological, anatomical, biomarker and intakerelated responses will be performed using R, SAS and other software. As part of the analysis, we will compute descriptive statistics for each variable. In particular, we will compute the proportion, mean, variance, standard error and the range of continuous variables and frequency and mode for discrete variables. Descriptive statistics will be computed for each specific sleep phase. In addition, correlation coefficients between the variables will be computed and scatter plots will be checked for linear relationships. The correlations and scatter plots help assess the degree of collinearity among variables, which will be useful for interpreting regression-based linear mixed model analyses discussed later. The data will be tested for normality, and if needed an appropriate transformation will be used on the raw data to make the normal approximation better. We will have a comprehensive strategy to deal with missing data. We will study missingness to decide if the data are missing at random or missing completely at random. Missing rates will also be estimated for each variable. Missing values will be imputed, as appropriate. We will fit a linear mixed model to analyze the data. Treatments (sleep duration: SR vs. HS) will be fixed effects and subjects a random effect. As we are collecting data from two phases for each subject, we will test for carryover effects by using a treatment x phase interaction in an initial version of each linear model. If the interaction term is not significant then we will rebuild the linear model without the interaction term. The other independent variables (covariates) will be sex, age, baseline BMI, and race/ethnicity. If required anywhere in the analysis plan, p-values will be adjusted for multiple comparisons. Sp. Aim 1: Hypothesis 1a. SR will lead to increased total adipose tissue mass, as assessed using MRI, relative to HS. We will perform repeated measure linear mixed model analyses separately for adipose tissue mass increase and weight gain (as the response). Sleep duration (SR vs. HS) and the covariates will be used as independent variables. Subject will be used as a random effect. Paired t-test and Wilcoxon test will be used to determine whether the SR and HS have different

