
effects on weight gain and adipose tissue mass increase. Hypothesis 1b. EE, assessed by DLW, and physical activity level, monitored daily by actigraphy, will be lower during SR relative to HS. We will perform repeated measure linear mixed model analyses separately for DLW and actigraphy-derived variables as the responses. Sleep duration (SR vs. HS) and the covariates will be used as independent variables. Subject will be used as a random effect. Paired t-test and Wilcoxon test will be used to determine whether SR and HS have different effects on DLW and actigraphy measures. Sp. Aim 2: Hypothesis 2a. EI, assessed by [3-d food records], will be greater during a period of SR relative to HS. This will be mostly due to increased fat and carbohydrate intakes. We will perform a repeated measure linear mixed model analyses separately with each EI measure (as the response) and sleep duration (SR vs. HS) and the covariates as independent variables. Subject will be used as a random effect. Paired t-test and Wilcoxon test will be used to determine whether the SR and HS have different effects on EI measures. Hypothesis 2b. Neural responses to food stimuli, assessed by fMRI after 6 wk of SR or HS, will indicate increased activity in networks associated with reward and food valuation (insula, orbitofrontal cortex) during a period of SR relative to HS. These responses will be correlated with intakes of high carbohydrate and high fat foods (hypothesis 1a) and [ghrelin]. Connectivity of the networks involved in reward valuation at rest will be stronger after SR compared to HS and synchrony of the DMN will be reduced after SR compared to HS. Sp. Aim 3: Hypothesis 3a. SR will lead to [increased glucose, insulin, triglycerides, and reduced highdensity lipoprotein cholesterol and adiponectin relative to HS.] We will perform repeated measure linear mixed model analyses separately for each of glucose, insulin, triglycerides, high-density lipoprotein cholesterol and adiponectin. Sleep duration (SR vs. HS) and the covariates will be used as independent variables. Subject will be used as a random effect. One-sided paired t-test and Wilcoxon test will also be used to determine whether the SR and HS have different effects on the cardio-metabolic risk profiles, as well as the direction of the effects. Hypothesis 3b. Increased adiposity and poor diet quality (higher fat and carbohydrates) after SR will partially explain the adverse cardio-metabolic risk profile associated with SR. We will select the cardiometabolic risk profile variables that are adversely associated with SR. Then, we will compute the difference in those variables in SR vs. HS (i.e. the value of each variable in SR minus the value of that variable in HS). Using a linear model analysis, we will test if these differences are associated with increased adiposity and poor diet quality. If, for some variables, there are multiple observed differences for each subject then a linear mixed model analysis will be used with subject as a grouping variable. A separate analysis will be performed for each such difference, with the difference as the response variables and adiposity, food quality variables and the covariates as dependent variables. *Linear Mixed Model Analyses.* We will fit a linear mixed model to analyze the data. Treatments (SR vs. HS) will be used as fixed effects and subject will be used a random effect. The other independent variables, such as demographic variables, will be covariates. Those covariates will be removed if they do not significantly contribute to the model. Aim 4: (To determine whether long-term mild SR, relative to HS, challenged acute cognitive outcomes in older and younger adults. Hypothesis 4a. Mild SR will induce cognitive decline, assessed using with the NIH Toolbox, which will be greater in older relative to younger adults.) Outcomes are measures from the NIH Toolbox. Each outcome will be analyzed in separate linear mixed model analyses, for older and young participants, as detailed in "*Linear Mixed Model Analyses*" section above. Sleep (SR vs. HS), along with phase (1 vs. 2), carryover effects, and covariates (if they are found to be significant in an initial analysis) will be used in the model. Subject will be used as a random effect. Then, we will pool the datasets to include both older and young participants. In the pooled dataset, we will use the average differences in NIH Toolbox measures (from HS to SR) as outcomes in linear model analysis. Age group (older vs. younger) will be used as main predictor variable. We will also apply covariates as independent variables, if they are found to be significant in an initial analysis. We will use unpaired t-test on the average difference in

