#### Assessment of metabolic parameters.

Fasting blood samples will be taken at baseline, wk 3, wk 4, and endpoint of each sleep phase for measuring lipid profile, glucose, insulin, adiponectin, leptin, ghrelin, and GLP-1. [92]. All samples will be analyzed in the Hormone and Metabolite Core laboratory of the NYORC (Dr. [name], Core laboratory Director) by skilled technicians. Insulin will be assayed using a radioimmunoassay (RIA; Linco Research Products Inc., St. Charles, MO; mean inter-assay CV 4.5% [93, 94]). Serum leptin will be measured using a double-antibody RIA (Linco Research; inter-assay CV 6.8% [93, 94]). Cortisol will be assay using enzyme immunoassay (DPC, Los Angeles, CA). 6-Sulfatoxymelatonin will be assayed from morning urine samples as a proxy for overnight melatonin production [95] using ELISA kit (ALPCO, Salem, NC). Blood samples will be collected in EDTA-coated chilled tubes for measuring peptide hormones. The tubes will be pre-treated with addition of aprotinin (0.6 TIU/mL of blood) and DPP-IV inhibitor (10 L/mL of blood) to prevent hormone degradation. Total ghrelin will be assessed using RIA (Linco Research; inter-assay CV 6.3% [96]). Adiponectin levels will be analyzed using RIA (Linco Research). GLP-1 will be assessed using RIA (Phoenix Pharmaceutical, Belmont, CA). An additional blood sample will be collected in silica-coated serum separating tubes to measure thyroid stimulating hormone, free T4, and sex hormones (testosterone, estrogen, progesterone, FSH, and LH).

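### Hypotheses 2a and 3a: with subject as the only random effect, the sleep test is too liberal if several visits per phase are analysed, and the plan does not say which visits are

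*Combined protocol and SAP*

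**What the plan says.** All of the following is in the combined protocol and SAP.

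- **Model.** Statistical Procedures gives 2a and 3a a repeated-measures linear mixed model. For 3a: "Sleep duration (SR vs. HS) and the covariates will be used as independent variables. Subject will be used as a random effect". The covariates are sex, age, baseline BMI and race/ethnicity. Also, "we will test for carryover effects by using a treatment x phase interaction in an initial version of each linear model", and the interaction is dropped if it is not significant. Only Aim 4 lists phase explicitly as a model term. No week term, subject-within-phase effect or residual covariance is given.
- **Number of values.** The sample-size text says only that "each response variable will be measured at least once per phase".
- **Intake visits.** Appetite & food intake measurements schedules food records at baseline, week 3 and week 6.
- **Marker visits.** Assessment of metabolic parameters says "Fasting blood samples will be taken at baseline, wk 3, wk 4, and endpoint of each sleep phase". Overview of Procedures has the same four fasting draws.
- **Differences.** Hypothesis 3b takes "the value of each variable in SR minus the value of that variable in HS", but also provides for the case where "there are multiple observed differences for each subject then a linear mixed model analysis will be used with subject as a grouping variable".
- **Cognition.** The NIH Toolbox is given at baseline and week 6. For the pooled Aim 4 analysis, "we will use the average differences in NIH Toolbox measures (from HS to SR) as outcomes in linear model analysis", with no statement of what is averaged. Aim 5 uses the same undefined quantity.
- **Second analysis.** 2a and 3a also get a paired t-test and a Wilcoxon test, again with no visit named.

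**The concern.** A subject intercept accounts for one person being generally higher than another. It does not account for a person being higher throughout one six-week phase than throughout the other, for reasons such as season, weight or individual response. Sleep condition varies only between phases, so that phase-level variation is the error against which the sleep effect should be judged. If two or three visits per phase enter with subject as the only random effect, the model judges sleep largely against visit-to-visit noise and counts repeated visits as extra independent evidence.

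At stake are the p-values for 2a and 3a. The planned paired tests hold their level when run on one difference per person, so the two planned analyses can disagree, and no rule says which decides. Hypothesis 3b carries forward the markers found to be adversely associated with SR. If that selection uses the 3a model, false positives carry into 3b.

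**Working it through.** **The plan's own figures.** Standardised intake effects are 295.9/116.3 = 2.54 (energy), 20.7/6.8 = 3.04 (fat) and 57.9/32.6 = 1.78 (carbohydrate). With 50 pairs and an assumed two-sided 5% level, paired t-test power exceeds 0.9999 for each, which agrees with the stated >80%. Halving the effects (1.27, 1.52, 0.89) still gives at least 0.999 at 36 pairs. Intake power is not in question. These calculations use one pair per person and do not describe a model with several rows per phase.

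**Inputs.** Completers: 36 (Subjects section); 50 were planned. Post-baseline visits per phase, *k*: 2 for intake, 3 for fasting markers, 1 for the Toolbox. Level: 5% two-sided, assumed because the plan states none. Ratio *w* = subject-by-phase variance / residual variance: assumed 0 to 1.0, because the documents give no value.

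**Standard error.** With residual variance s², one person's difference between two phase means has variance (2s²/k)(1 + kw). The subject-only model pools 2k-1 within-subject degrees of freedom. One of these (between phases) has mean square s²(1 + kw) and the other 2k-2 have s², so the average is s²[1 + kw/(2k-1)]. Hence

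model SE / true SE = sqrt{ [1 + kw/(2k-1)] / (1 + kw) }.

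Example, k = 3, w = 1: sqrt(1.6/4) = 0.632. The approximate type I error is 2[1 - Φ(1.96 × 0.632)] = 21.5%.

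**Type I error.** 20,000 simulated two-period crossovers per cell, n = 36, phase in the model:

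| w (assumed) | k=2: SE ratio | k=2: type I | k=3: SE ratio | k=3: type I |
|---|---|---|---|---|
| 0 | 1.00 | about 5% | 1.00 | about 5% |
| 0.1 | 0.943 | 6.5% | 0.903 | 7.7% |
| 0.25 | 0.882 | 8.3% | 0.811 | 11.5% |
| 0.5 | 0.816 | 10.9% | 0.721 | 15.7% |
| 1.0 | 0.745 | 14.6% | 0.632 | 22.0% |

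At n = 50 the ranges for w = 0.1 to 1.0 are 6.7-14.6% and 7.7-20.9%, so sample size hardly matters. With k = 1 the SE ratio is 1 for every w.

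**Check that the correction works.** Testing one phase-mean difference per person on the same data gives 4.7-5.2%. In a REML fit (n = 50, k = 3, 30% of within-subject variance shared by a phase's visits, so w = 0.3/0.7 = 0.43; 250 runs), the subject-only model rejected in 15.6% and the model with a subject-by-phase term in 5.6%.

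**Use of the phase baseline.** If all subject-by-phase variance is already present at baseline, the baseline and week-6 SR-HS differences correlate at r = w/(1 + w) = 0.09 to 0.50. Regressing one on the other multiplies the week-6 standard error by sqrt(1 - r²) = 0.996 to 0.87. If that variance arises only after baseline, r = 0 and nothing is gained. A single raw baseline slope in the random-subject model behaves differently, because it mixes between- and within-subject slopes. In REML simulations (n = 36, one post-baseline visit, subject variance 1, 2 or 4 times residual), its standard error relative to week 6 alone was 1.07, 1.14 and 1.22 at w = 0.1, and 0.88, 0.93 and 0.97 at w = 1.0.

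**The case against.** The strongest reply is that the plan intends one value per phase. It specifies paired tests, counts 50 × 2 paired observations, and describes 3b through "the value of each variable in SR minus the value of that variable in HS". With one value per phase a subject random effect is adequate and nothing is inflated. This stands as a limit on the point: the plan leaves the choice open and does not commit to a faulty analysis. It does not dispose of the point, because the plan also calls the models repeated-measures, counts at least one measurement per phase, and expects several differences per person in 3b. The variance ratio has no source in the documents either, so 22% is illustrative.

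A reader might infer more than the documents support:

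- **That 4a is inflated too.** The Toolbox has one post-baseline visit per phase, so it is not. Only the averaged difference in Aims 4-5 is undefined.
- **That phase-baseline rows will be analysed as responses, diluting the effect.** The text does not exclude this, but it is not a stated plan.
- **That leaving out the phase baseline biases the result.** With randomised order it is at most a loss of precision, and the obvious remedy of one raw baseline slope can make precision worse.
- **That the blood schedules conflict.** Study Design says "fasting blood and urine samples will be taken at baseline, week-3, and endpoint, during adherence check visits", omitting week 4, but the same section later adds a fasting blood sample at week 4, before the doubly labelled water dose. The sentence is incomplete; the schedule is not contradictory on this point.
- **That results already reported are wrong.** The documents do not say how those outcomes were analysed.

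**Conclusion.** The point holds in conditional form for 2a and 3a. If all post-baseline visits enter the model as written, a nominal 5% test of sleep runs at about 6.5-14.6% for intake (two visits) and 7.7-22% for fasting markers (three visits). This assumes a subject-by-phase to residual ratio of 0.1 to 1.0, complete balanced data and equal correlation among visits within a phase. At ratio 0, or with one value per phase, the error is about 5%. The visit must be named in either case, because the paired tests need it too. Hypothesis 4a has no inflation, but the averaged difference in Aims 4-5 needs a definition. This should be fixed: the correction costs almost nothing, and the plan as worded permits both a valid and a too-liberal analysis.

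**What to change.** 1. State that only post-baseline values are responses, and name the visits.
2. Where more than one visit per phase enters 2a or 3a, add week and a subject-within-phase random effect, or analyse one summary per phase (week 6 or the phase mean, chosen in advance). Keep phase in the model.
3. Where 3b uses several differences per person, name the visits and add week, or use the same single summary. Its response is already an SR-HS difference, so its subject intercept carries the phase-level variation.
4. Use the same SR-HS difference in the paired tests, and define the averaged differences of Aims 4-5 by it.
5. Optional, for precision: regress the SR-HS difference on the SR-HS difference in phase baselines, or centre the phase baseline within subject and include the subject mean as a separate term. Do not enter one raw phase-baseline slope. The gain is about 0-13% of the week-6 standard error, and only if the subject-by-phase variance already exists at baseline. Use the baseline food record this way only if it precedes the first assigned night; its dates are not given.

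The cost is SAP wording and a few degrees of freedom; no new data collection is needed. Enrolment is closed, lipid and inflammatory-marker results are published and a cognition paper is in press, so any re-analysis of reported outcomes must be labelled post hoc.

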activity in networks associated with reward and food valuation (insula, orbitofrontal cortex) during a period of SR relative to HS. These responses will be correlated with intakes of high carbohydrate and high fat foods (hypothesis 1a) and ghrelin. Connectivity of the networks involved in reward valuation at rest will be stronger after SR compared to HS and synchrony of the DMN will be reduced after SR compared to HS. **Aim 3:** Does Longer, milder SR, as observed in individuals with SSD adverse cardiometabolic risk profile? **Hypothesis 3a:** SR will lead to increased glucose, insulin, triglycerides, and reduced high density lipoprotein cholesterol and adiponectin relative to HS. **Hypothesis 3b:** Increased adiposity and poor diet quality (higher fat and carbohydrates) after SR will partially explain the adverse cardio-metabolic risk profile associated with SR. **Aim 4.** To determine whether long-term mild SR, relative to HS, challenges acute cognitive outcomes in older and younger adults. **Hypothesis 4a.** Mild SR will induce cognitive decline, assessed with the NIH Toolbox, which will be greater in older relative to younger adults. **Aim 5.** To determine whether the effects of SR on cognitive outcomes are moderated by brain atrophy and small vessel cerebrovascular disease in younger and older adults. **Hypothesis 5a.** The effect of mild SR on cognition will be greater among individuals with greater amounts of cortical thinning, smaller hippocampi, and greater WMH volume. This effect will be larger in older relative to younger adults. **Aim 6.** To determine whether changes in metabolic or hormonal profiles mediate changes in cognitive function as a result of SR. **Hypothesis 6a.** The effect of mild SR on cognition will be mediated by changes in hormones (leptin, adiponectin, and insulin).

---

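### Hypothesis 3b states a mediation claim, but its only named test is a slope across participants, which is the same whether or not SR changes adiposity or diet on average.

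*Combined protocol and SAP*

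**What the plan says.** All of this is in the Combined protocol and SAP, under Statistical Procedures, Sp. Aim 3, unless noted.

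- **The claim.** "Increased adiposity and poor diet quality (higher fat and carbohydrates) after SR will partially explain the adverse cardio-metabolic risk profile associated with SR". The section Research Question(s)/Hypothesis(es) repeats it.
- **Which markers go forward.** "We will select the cardiometabolic risk profile variables that are adversely associated with SR".
- **The response.** A within-person difference: "the value of each variable in SR minus the value of that variable in HS".
- **The test.** "Using a linear model analysis, we will test if these differences are associated with increased adiposity and poor diet quality".
- **The model.** One analysis per marker, "with the difference as the response variables and adiposity, food quality variables and the covariates as dependent variables". The last two words are evidently a slip for independent variables. The sentence does not say whether adiposity and diet enter as SR minus HS differences or as levels.
- **What is tested elsewhere.** Hypothesis 1a tests the mean SR effect on adipose tissue mass and weight. Hypothesis 2a does the same for intake: "Paired t-test and Wilcoxon test will be used to determine whether the SR and HS have different effects on EI measures". Neither result is referred to in 3b.
- **A contrast.** For Aim 6, also a mediation question, sleep must significantly affect the hormone before the final step is run, and the plan states when mediation is concluded.

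**The concern.** To explain part of the SR effect, a mediator must meet two conditions: SR must move it on average, and its change must be related to the marker change. The explained amount is the product of the two. The analysis listed for 3b addresses only the second. People whose fat mass rises more may well show larger rises in triglycerides or insulin whatever their sleep schedule, and that ordinary covariation is enough to produce a significant slope.

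If adiposity or diet entered as a level, the slope would instead show whether fatter or worse-fed participants respond more to SR. That is moderation, a different question.

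At stake is a mechanistic statement, that SR harms risk markers through fat gain and diet, made from a result that would look the same if SR had caused no fat gain and no change in diet. The tests of 1a, 2a and 3a themselves are unaffected.

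**Working it through.** **1. The plan's nearest figure.** No power or sample size is stated for 3b. The plan does give standardised SR effects for fat mass and weight: 0.69/0.36 = 1.92 and 0.91/0.65 = 1.40. Both reproduce. With 50 completers, the smaller one gives 1.40 × √50 − 1.96 = 7.9, so power above 99% also reproduces. The plan therefore expects a large mean shift in adiposity, but it estimates that shift from 2 women in a pilot.

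**2. What the 3b test depends on.** Let D be a participant's marker difference and M the mediator difference, in SD units:

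D = c′ + b·M + error, so mean(D) = c′ + b × mean(M).

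The explained part is b × mean(M), and the unexplained part is the intercept c′. Adding a constant to every M changes c′ but leaves b and its p-value unchanged. The test of b therefore carries no information on mean(M). With b = 0.3 and a total effect of 0.5 SD:

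- mean(M) = 0: explained part 0.3 × 0 = 0.
- mean(M) = 1.92 (the plan's figure): explained part 0.3 × 1.92 = 0.576 SD, more than the whole total effect.

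The test result is identical in the two cases. A simulation of 20,000 trials per setting with three predictors (adiposity, fat intake, carbohydrate intake) confirms this. At n = 50 the slope test was positive in 58%, 83% and 96% of trials with a selected marker, for correlations of 0.3, 0.4 and 0.5. It did so both with zero mean shift and with the plan's shifts of 1.92, 3.04 and 1.78. With zero shift, the average share explained was −0.01 to 0.00 and the intercept stayed at about 0.51 SD.

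**3. How often a slope appears when nothing is explained.** Inputs from the documents are 50 planned completers (Statistical Procedures) and 36 reported completers (Subjects; not split by age group). Assumed inputs are a 0.5 SD marker effect, zero mean mediator change, correlation r between the two changes, and alpha 0.05 two-sided for the slope. Selection is a significant adverse paired test; the plan's one-sided version passes about 90% of trials at n = 36 and 97% at n = 50.

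The Fisher approximation is Φ(atanh(r)·√(n−3) − 1.96). For r = 0.3 and n = 36: 0.3095 × 5.745 = 1.778, and Φ(−0.182) = 0.428.

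| r | n = 36, Fisher | n = 36, simulated | n = 50, Fisher | n = 50, simulated |
|---|---|---|---|---|
| 0.1 | 8% | 8% | 10% | 10% |
| 0.2 | 21% | 22% | 28% | 29% |
| 0.3 | 43% | 42% | 56% | 57% |
| 0.5 | 88% | 89% | 97% | 96% |

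At r = 0 the simulated rate is 2.5% at n = 36, counting positive slopes for one mediator.

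**4. What a repaired rule does.** In the same zero-shift setting at r = 0.3 and 0.5, two rules each claim explanation in about 1% to 3% of trials. One is a bootstrap interval for mean(M) × b lying above zero. The other is a significant slope plus a significant rise in the same mediator. With real mediation (mediator shift 0.5 SD, r = 0.5, n = 36) the bootstrap rule detects it in 78%.

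**The case against.** The strongest reply is that 3b contains no decision rule. It says an association will be tested, not that a significant slope settles the matter. Where the plan wants a rule it writes one, as in Aim 6. A reader might infer that the plan commits to declaring mediation from the slope alone, and the documents do not support that. What stands against the plan is narrower: nothing else is named that would connect the data to the claim.

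Second, the missing step is tested under 1a and 2a, and the wording of 3b presumes increased adiposity after SR. Authors who found no fat gain would have to overlook their own result to make the claim. This is fair, and joining the slope to those results does repair the problem (step 4). But the plan does not make that link, and it does make it in Aim 6.

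Third, the percentages follow from the assumed r. They are in essence the power of a correlation test, and no correlation is given in the documents. A reader might take 42% or 89% as the trial's actual false-claim rate, which would be wrong; only the mean-invariance of the slope is independent of assumptions.

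Fourth, a reader might count the restriction to adversely affected markers as a further fault. It is not one: the hypothesis concerns "will partially explain the adverse cardio-metabolic risk profile associated with SR", so there is nothing to explain in other markers.

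**Conclusion.** The concern holds in this form: the analysis listed for 3b cannot separate the hypothesis from its absence, because its one test ignores the mean SR effect on the mediator, and the text links it to neither 1a nor 2a. The screening of markers does not help, since it involves neither adiposity nor diet. The unstated form of the predictors adds to the problem, because levels would test moderation.

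If a significant positive slope were taken as sufficient, claims with nothing explained would arise in about 8% to 89% of trials at 36 completers and 10% to 96% at 50, over assumed r from 0.1 to 0.5. These ranges rest on the 0.5 SD marker effect, zero mean mediator change and alpha 0.05, all assumed.

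Severity is should-fix. Hypothesis 3b is secondary and explanatory; the error would be one of interpretation. Nor do the documents show that a faulty 3b claim has been published: the renewal section lists published lipid and inflammatory data and a cognitive paper in press, and mentions no 3b result.

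**What to change.** In the 3b paragraph of Statistical Procedures:

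1. Enter adiposity and diet as SR minus HS differences, uncentred, and correct the slip that calls the predictors dependent variables.
2. For each adversely affected marker, report the indirect effect: phase-adjusted mean mediator difference × slope, with a bootstrap interval that resamples participants. Use the same phase term and centred covariates in the mediator and marker models, so that the intercept is the unexplained SR effect. Phase adjustment matters. With an assumed 0.5 SD phase effect on the mediator and a 24/12 split of sequences at n = 36, the unadjusted version claims mediation in 13% of null trials; with 20/16 it stays near 2%.
3. Conclude that a mediator partially explains the effect only if that interval excludes zero in the direction of the total effect. A simpler rule that performs about as well is to require a significant slope and a significant SR increase in that same mediator under 1a or 2a. Otherwise, report only that the changes are correlated across participants.
4. State that the mediator-to-marker slope is not randomised and remains open to confounding even under the repaired rule.
5. State that the change is post hoc for the lipid markers already published.

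The cost is SAP wording and a few lines of code. No new data are needed, which suits a study now open only for analysis and reporting. The downside is that fewer explanatory claims will be made.
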